2.0 OBJECTIVES AND SCIENTIFIC AIMS

2.1 Primary Objectives

- To determine feasibility, safety and tolerability of single dose administration of ⁸⁹Zr-DFO-MSTP2109A antibody.
- To determine the ability of ⁸⁹Zr-DFO-MSTP2109A PET to detect sites of metastatic prostate cancer.
- To determine the pharmacokinetics (PK) and biodistribution of ⁸⁹Zr-DFO-MSTP2109A.

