12.0 CRITERIA FOR THERAPEUTIC RESPONSE/OUTCOME ASSESSMENT

Positive lesions on ⁸⁹Zr-DFO-MSTP2109A will be defined visually as a focus of accumulation of radioactivity that is deemed to not be physiologic and is higher than adjacent or contralateral background. Antibody scan will be read blinded from clinical history and conventional imaging modalities. Two different experienced, blinded readers will visually analyze the ⁸⁹Zr-DFO-MSTP2109A scans, and SUVmax/mean will be determined in lesions identified and in normal organs and blood pool. To study the accumulation and biodistribution of ⁸⁹Zr-DFO-MSTP2109A in patients with progressive prostate cancer, the accumulation of ⁸⁹Zr-DFO-MSTP2109A will be assessed for each site and compared with the baseline radionuclide bone scan, FDG PET/CT, CT, and/or MRI imaging. The definition of a positive lesion will be a lesion identified by an experienced reader on conventional imaging CT/MRI, bone scan, and/or FDG scan consistent with metastatic disease, as is currently done clinically. Lesions on ⁸⁹Zr-DFO-MSTP2109A or conventional imaging will be read in a scale of 1 to 5, 1= negative, 2 = probably negative, 3= not sure, 4= probably positive and 5= definitively positive. Once this is done, a consensus master list of lesions will be created that compares all imaging conventional imaging modalities(CT/MRI, FDG PET, bone scan), only those lesions that are conspicuously positive (i.e., "4 or 5") by imaging will be considered as a positive site of disease. Discrepant findings between findings on conventional imaging and ⁸⁹Zr-DFO-MSTP2109A modalities will be considered false positive or false negative. Although it would be ideal to biopsy any site that is considered abnormal this is not logistically feasible or ethically acceptable. Successful imaging will be considered a sensitivity of detection of $\geq 75\%$ of patients that are STEAP1 positive. One or 2 non-blinded readers (access to clinical, laboratory and imaging data) will identify "positive lesions".

As a first level, we will compare site by site. Since the individual modalities are based on different mechanisms of uptake, they may not have exact correspondence in space, since bone scan is a 2D modality and looks at bone reaction and ⁸⁹Zr looks at tumor antigen expression and is a 3D modality.

For this purpose, we have made a list of standardized anatomic sites, to make sure that a positive

MEMORIAL SLOAN-KETTERING CANCER CENTER IRB PROTOCOL

IRB#:12-178 A(3)

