lesion would have a positive ^{89}Zr -DFO-MSTP2109A uptake. As a second level, we will compare lesion by lesion. Sensitivity and specificity of the imaging modalities will be compared in those patients receiving the better/"adequate" antibody mass. The "better/adequate" dose is defined as that which will allow us to visualize the targeted number of lesions defined and will consist of either 10 or 20 mg of DFO-MSTP2109A antibody.

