12.1 Bone Scan

Each lesion will be evaluated using the same 5-point scale. These findings will be compared with that of ^{89}Zr -DFO-MSTP2109A PET scanning.

Any discrepant reading of the antibody images or conventional images will require review of the images by both readers who will discuss and reach a consensus, if a consensus cannot be reached the finding shall be considered "not sure" and categorized as negative.

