12.2 CT and MRI

Available CT and/or MRI imaging done clinically will be used as a correlative diagnostic imaging tool to compare to results of ^{89}Zr -DFO-MSTP2109A PET scanning. Sensitivity of ^{89}Zr -DFO-MSTP2109A PET scanning to detect lesions will be compared with routine imaging including CT, MRI, FDG PET, and bone scans. Furthermore soft tissue lesions greater than 2 cm on CT or MRI will also be compared to ^{89}Zr -DFO-MSTP2109A in order to overcome the issues of partial volume.

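### Section 12 scores the tracer against a lesion list built only from the scans it is compared with, so the planned sensitivity and specificity contrast is neither a ranking nor specificity for disease

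*Combined protocol and SAP*

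**What the plan says.** All references are to the combined protocol and SAP.

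- **Reference.** Section 12.0: "The definition of a positive lesion will be a lesion identified by an experienced reader on conventional imaging CT/MRI, bone scan, and/or FDG scan". After 5-point scoring, "a consensus master list of lesions will be created that compares all imaging conventional imaging modalities(CT/MRI, FDG PET, bone scan"; only lesions scored 4 or 5 count as positive. The tracer is not a component. The plan does not say whether one positive scan is enough for listing.
- **Disagreements.** Discrepancies between conventional imaging and the tracer "modalities will be considered false positive or false negative".
- **Truth standard.** Section 12.0 rules out biopsy of every abnormal site on practical and ethical grounds.
- **Comparison.** Section 12.0: "Sensitivity and specificity of the imaging modalities will be compared in those patients" receiving the better or adequate mass. Section 12.1, on bone scan: "Each lesion will be evaluated using the same 5-point scale. These findings will be compared with that of" the tracer. Section 12.2 says the sensitivity of the tracer scan "to detect lesions will be compared with routine imaging including CT, MRI, FDG PET, and bone scans".
- **Purpose.** Section 2.1 includes as a primary objective the ability of the tracer "PET to detect sites of metastatic prostate cancer". Section 5.0 says that detection relative to standard imaging will be explored.

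No test, margin or power is attached to the comparison between modalities.

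**The concern.** The comparators are part of their own reference standard, and the standard is imperfect. This is incorporation bias. A lesion that only the tracer sees cannot be a true positive under the section 12.0 definition, because that definition names conventional scans only.

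The protocol's own rationale makes such lesions plausible. Section 1.0 says bone scintigraphy shows the reaction of bone rather than the tumour, and section 3.1.2 says CT misses small nodal disease. Section 14.2 admits that the conventional list may contain false positives, but uses this only to support the 20% lesion threshold. No section says how disease missing from the list affects the comparison.

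Section 12 is the only place that plans site-level and lesion-level sensitivity and specificity. Read at face value, its output could describe a tracer that finds real additional disease as less specific, and could shrink, reverse or in some cases inflate its lead in sensitivity.

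**Working it through.** **The plan's own figures.** None is given for this comparison. The nearest are in section 14.2, and they reproduce: the half-width at n = 15 and 75% is 1.96 × √(0.75 × 0.25/15) = 0.219 (stated 22%), and the chance of opening Cohort 1B under the 4-of-6 rule is 0.821 at 40% and 0.169 at 75% (stated more than 82% and less than 17%). They concern other analyses and are not in dispute.

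**Inputs.** The documents give no accuracies, prevalence, dependence between scans or listing rule. All values below are assumptions for illustration: tracer sensitivity t = 0.70; each scan s = 0.60; 30% or 50% of sites diseased. FDG PET is on the section 12.0 list but not in the baseline imaging of section 8.1 or Table 2 (footnote d), so both two and three scans are shown.

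**Sensitivity, general form.** Among true lesions, let L be the share listed, o the share that is tracer-positive but off the list, and c the share positive on a given scan but off the list. With no false positives listed:

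observed lead = [(t − o) − (s − c)] / L

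This is below the true lead t − s when (o − c)/(1 − L) > t − s. If one positive scan is enough, c = 0. The lead is then understated when the tracer finds a larger share of off-list disease than the lead itself (here, more than 10%), and overstated when it finds a smaller share.

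*Largest overstatement* (o = 0):
- Without assuming independence, L can be as small as t, giving 0.10/0.70 = +14.3 points.
- With two independent scans, L = 1 − 0.4² = 0.84, giving 0.10/0.84 = +11.9 points.

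**Sensitivity with independent reads** (the tracer scores 0.70 against the list; true lead +10):
- Any-positive, two scans: scan 0.60/0.84 = 0.714; lead −1.4.
- Any-positive, three scans: L = 1 − 0.4³ = 0.936; scan 0.60/0.936 = 0.641; lead +5.9.
- Two of three: L = 3 × 0.6² × 0.4 + 0.6³ = 0.648; scan 0.6 × (1 − 0.4²)/0.648 = 0.504/0.648 = 0.778; lead −7.8. Here c = 0.6 × 0.4² = 0.096 and c/(1 − L) = 0.273, so the lead is understated only if the tracer finds more than 37.3% of off-list disease.

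Suppose 10% of listed lesions are not disease, each called by one scan and missed by the tracer. Any-positive listing then gives 0.630 − (0.9 × 0.714 + 0.1/2) = −6.3 points with two scans, and 0.630 − (0.9 × 0.641 + 0.1/3) = +2.0 points with three.

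**Specificity.** Suppose no modality ever calls a disease-free site, so true specificity is 100% for all. With prevalence p and d = (1 − p) + p(1 − L):

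tracer = 1 − p × 0.7 × (1 − L)/d; scan = 1 − p × c/d

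| Listing rule | Tracer, p = 30% / 50% | Each scan, p = 30% / 50% |
|---|---|---|
| Any-positive, two scans | 95.5% / 90.3% | 100% / 100% |
| Any-positive, three scans | 98.1% / 95.8% | 100% / 100% |
| Two of three | 90.8% / 81.8% | 96.4% / 92.9% |

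The tracer's figure falls in every row. The scans stay at 100% only under any-positive listing.

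**Check with equal accuracy.** Give the tracer and three independent scans the same 80% sensitivity and 95% specificity, with p = 30% and any-positive listing. The listed share of sites is 0.3 × 0.992 + 0.7 × 0.1426 = 0.3974. A scan scores (0.24 + 0.035)/0.3974 = 69.2% sensitivity and 100% specificity; the tracer scores 61.2% and 94.7%. Under two of three, the scan scores 85.4% and 94.3%, the tracer 78.6% and 91.8%. If the tracer copies one scan half the time, the gaps roughly halve but keep their sign.

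**The case against.** **No ranking may be intended.** The head-to-head reading rests on the plural in section 12.0 together with 12.1 and 12.2. The sentence just before it concerns checking that listed lesions show tracer uptake, and 12.2 can be read as making routine imaging the reference. Neither the objectives (2.1, 2.2) nor section 14 asks for a ranking. This stands as a limit on the claim. Even so, scoring the tracer against the list leaves the false-positive label and the word specificity unsupported.

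**The authors knew that no truth standard was available.** They say universal biopsy cannot be done and that the modalities may not correspond in space. That is true, but neither remark changes how discrepancies are scored.

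**Safeguards exist.** Blinded tracer reading and the consensus step in 12.1 address reader bias, not who forms the list. The pathology correlation in 9.3 concerns STEAP1 presence, not adjudication of lesions. Section 12.0 adds: "One or 2 non-blinded readers (access to clinical, laboratory and imaging data) will identify" positive lesions. A tracer-only lesion might enter the list that way, but no rule provides for it and the definition names only conventional scans.

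**The direction is not fixed.** This is correct for sensitivity. If the tracer misses the same lesions as the scans, its lead is overstated. Shared misses are plausible, since 12.2 itself raises partial-volume limits. The specificity contrast can also fall either way under two-of-three listing: against scans at 60% sensitivity and 90% specificity, a perfect tracer scores 91.7% against 90.1% per scan at 20% prevalence, but 73.4% against 86.6% at 50%.

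**Conclusion.** The point holds in a limited, descriptive form. The conventional scans help build the reference and the tracer does not, so the section 12 results support neither a ranking of modalities nor a claim about specificity for disease. The firmest part is that real disease seen only by the tracer lowers its apparent specificity whatever the listing rule. The sensitivity contrast usually, but not always, favours the listed scans. The size is unknown; every figure for the contrast rests on assumed accuracies, and most also on independent reads.

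Three stronger readings are not supported:
- *The tracer will always look worse.* A true 10-point lead can appear as up to +14.3 points under the assumptions shown.
- *Every conventional scan scores 100% specificity by construction.* That needs any-positive listing, which the plan does not state.
- *The primary decisions are biased by this.* The 4-of-6 rule, the Cohort 1B stopping rule and the Cohort 2 proportion (section 14.2) count only conventionally identified lesions, so tracer-only lesions and the contrast between modalities do not enter them.

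**What to change.** In sections 12.0 and 12.2:

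- Report tracer results as positive and negative agreement with the conventional-imaging list, with patient-clustered intervals (14.3 already adjusts lesion uptake for clustering).
- Do not rank the tracer against scans that form the list.
- Replace false positive for tracer-only lesions with *unconfirmed*. Tabulate them by patient and site, and annotate them with pathology where it already exists.
- Report negative agreement with unconfirmed lesions counted as disagreements, and state that it is not specificity for disease.
- State how many positive scans place a lesion on the list.
- Leave the patient-level 75% criterion unchanged.

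Positive agreement is numerically the same as sensitivity against this list; what changes is the claim made from it. The cost is wording, tabulation and some abstraction of existing pathology, with no added scans, biopsies or patients. The downside is that no head-to-head ranking or specificity claim is reported, the comparative aim in section 5.0 is answered only as agreement, and some tracer-only lesions stay unresolved.

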12.1 Bone Scan

Each lesion will be evaluated using the same 5-point scale. These findings will be compared with that of ^{89}Zr -DFO-MSTP2109A PET scanning.

Any discrepant reading of the antibody images or conventional images will require review of the images by both readers who will discuss and reach a consensus, if a consensus cannot be reached the finding shall be considered "not sure" and categorized as negative.

12.2 CT and MRI

Available CT and/or MRI imaging done clinically will be used as a correlative diagnostic imaging tool to compare to results of ^{89}Zr -DFO-MSTP2109A PET scanning. Sensitivity of ^{89}Zr -DFO-MSTP2109A PET scanning to detect lesions will be compared with routine imaging including CT, MRI, FDG PET, and bone scans. Furthermore soft tissue lesions greater than 2 cm on CT or MRI will also be compared to ^{89}Zr -DFO-MSTP2109A in order to overcome the issues of partial volume.

13.0 CRITERIA FOR REMOVAL FROM STUDY

Participation in the study is strictly voluntary. Patients have the right to withdraw from the study at any time. If a patient chooses to withdraw, he or she must inform the investigator immediately. In addition, the investigator has the right to terminate participation of any patient at any time if it is deemed in the patient's best interest. The reason and circumstances for premature discontinuation will be documented in the patient's medical records. Possible examples for reasons of premature study withdrawal include withdrawal of consent, SAE or intolerable AE, or any other medical illness at investigator's discretion.

14.1 BIOSTATISTICS

14.2 Primary Objective

The primary objective of this protocol is to determine the feasibility, safety and tolerability of single dose administration of ^{89}Zr -DFO-MSTP2109A antibody.

A patient with STEAP1 positive tumor will be considered antibody-imaging-positive if 20% or more of the active lesions are detectable (STEAP1 positivity is an eligibility criterion for protocol 11-016 which forms the basis of eligibility for this protocol; see section 6 for details). Active lesion means any lesion that was identified by conventional imaging methods and clinical data at baseline. We have selected a low threshold of 20% for this first imaging study for 3 reasons: 1) we do not know what the heterogeneity of antigen expression is within a number of lesions in the same patient; 2) we will consider positive any lesion based on conventional clinical imaging criteria, in which case some lesions considered positive may be false positive and more importantly 3) our main emphasis is to evaluate whether patients whose tumor images are positive with ^{89}Zr -DFO-MSTP2109A are more likely to have a response to the antibody based drug conjugate used under

MEMORIAL SLOAN-KETTERING CANCER CENTER IRB PROTOCOL

IRB#:12-178 A(3)

protocol 11-016. Thus, we do not want to discard this agent if we can use it as a **theranostic** (defined as an agent that is integrated into the drug development process so as to guide patient selection and drug development) for the development of the antibody base drug conjugate being used under protocol 11-016. Nonethe less, we intend to evaluate treatment response of all available lesions in this way we will maximize our ability to determine the relationship between uptake of antibody and response.

If, for any patient, there is evidence of an “antigen sink” based on rapid clearance < 50 h or $Vd > 3$ times plasma volume, we will consider a patient antibody-imaging-positive if 20% or more of the active lesions are visualized. The presence of an “antigen sink” may bind a significant amount of antibody and make less available for binding to tumor.

Antibody imaging will be considered feasible if 75% of the patients are antibody-imaging-positive as defined above..We will enroll 6 patients (cohort 1A) at the 10mg dose level for an initial decision on feasibility. If 4 or more of these patients have 20% or more of their active lesions detectable by ^{89}Zr -DFO-MSTP2109A then we will consider the agent feasible for imaging, otherwise we will proceed to cohort 1B. If the true feasibility rate is 40%, this rule will affords more than 82% chance that cohort 1B will be opened for enrollment; this probability is less than 17% if the true feasibility is 75%. We will also require that none of these patients experience dose severe toxicity attributable to the initial 10 mg dose before cohort 1B is opened for enrollment.

If severe adverse effect (grade 3 or 4 CTCAE) is observed in any cohort we will review with MSKCC-DSMC and IRB before continuing with accrual. If 3 patients in cohort 1A do not show acceptable imaging, as described above, we will proceed to cohort 1B.

In cohort 1B, 6 more patients will be enrolled at a higher dose (20mg) for safety and pharmacokinetic evaluation. Serial blood draws will be used to estimate the pharmacokinetic profile of the 10 and 20mg ^{89}Zr -DFO-MSTP2109A in this patient population. Pharmacokinetic analysis will be performed using a non-compartmental analysis; standard parameters such as AUC, clearance, volume of distribution, and Co will be reported. Descriptive statistics will be tabulated. If 3 patients in Cohort 1B have antibody negative imaging accrual will stop. If 4 patients in cohort 1B have positive imaging we will move to cohort 2 using the best imaging dose from cohort IA or 1B..

Based on pharmacokinetic analysis from cohorts 1A and 1B an optimal time point (based visually on optimal image quality for tumor detection and clinically/logistically feasible) will be determined for imaging and cohort 2 will enroll up to 15 patients at the dose also determined from cohorts 1A or 1B. These patients will undergo a single whole-body scan at the optimal time point. The ability of ^{89}Zr -DFO-MSTP2109A to detect tumors will be estimated from this cohort using the proportion of antibody-imaging-positive patients (within +/-22% if the true detection rate is 75%).

This study does not intend to find the maximal tolerated dose of DFO-MSTP2109A. This is a diagnostic agent that is expected to have low incidence of adverse events. Patients will be monitored closely looking for evidence of adverse events. Because patients will likely start new therapies within 2 weeks of receiving ^{89}Zr -DFO-MSTP2109A only short term toxicity will be evaluated. The safety and tolerability of ^{89}Zr -DFO-MSTP2109A will be assessed using the following primary safety outcome measures: Incidence and nature of incidence, nature, and severity of adverse events; and change in vital signs and clinical laboratory results. Incidence and

MEMORIAL SLOAN-KETTERING CANCER CENTER IRB PROTOCOL

IRB#:12-178 A(3)

severity of adverse events will be summarized with descriptive statistics.

Dosimetry: SUVmax/mean (that can easily be converted to %ID/g) in normal organs of patients from Cohort 1A and Cohort 1B will be determined and this data over time will be used to determine the residence time in each visualized organ (liver, spleen, kidney and lung), other organ will be evaluated if clinically appropriate. The median residence time value will be used in OLINDA software to calculate the dosimetry.

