3.0 BACKGROUND AND RATIONALE

3.1 The Problem Being Addressed: Limitations of Conventional Imaging Modalities for Prostate Cancer Metastases

Progressive prostate cancer spreads to bone more commonly than to any other site, yet monitoring bone metastases to quantify cancer regression and progression remains inconsistent at best. In addition, a significant percentage of patients have soft tissue, predominant nodal disease. The standard Phase II response criteria for solid tumors do not apply, and despite the rapid evolution of imaging modalities for prostate cancer, visualizing of tumor spread to bone is still in the early stages of development. For example, as seen on plain radiographs, when prostate cancer spreads to bone, tumor growth in the marrow results in osteoblastic changes, which, in the end stage, result in the complete replacement of the marrow space. While most physicians accept that sclerotic healing of a lytic lesion constitutes tumor regression, sequential monitoring of lesions that are initially sclerotic is problematic because the bone architecture rarely reverts histologically back to normal. Even if all tumor cells are destroyed, there may be no visible changes on standard scans. In these cases, only a direct biopsy can determine if viable tumor cells are present. Other imaging modalities have significant limitations in identifying viable tumor as described below. Immunotherapy, radioimmunotherapy or antibody drug conjugate (ADC) related therapy are dependent on targeted antigen concentration. While patients may be selected based on antigen expression based on tumor biopsy, this is an invasive technique and is limited by impracticality of multiple tumor biopsy. In contrast, using a radiolabeled antibody approach allows one to non invasively select patients based on antigen content and allows assessment of multiple tumor sites.

Imaging modalities in prostate cancer

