6.1 CRITERIA FOR SUBJECT ELIGIBILITY

6.2 Subject Inclusion Criteria

To be included in this study, patients should be eligible for enrollment into protocol 11-016 (therapy with the DSTP3086S ADC) or meet all of the following criteria:

- Patients meeting the criteria for enrollment on research protocol 11-016 to receive

MEMORIAL SLOAN-KETTERING CANCER CENTER IRB PROTOCOL

IRB#:12-178 A(3)

DSTP3086S ADC (therapeutic ADC based on MSTP2109A) will be the preferred patients for this study. Patients that are to receive DSTP3086S will not be injected with DSTP2086S until imaging with ⁸⁹Zr-DFO-MSTP2109A is finished, approximately 1 week.

- Adult male >21years of age
- Visible lesions by either CT, bone scan or MRI consistent with metastatic disease
 - Metastatic progressive disease
 - Imaging modalities:
Bone scan: new osseous lesion and/or
MRI or CT: An increase in measurable soft tissue disease or the appearance of new sites of disease.

Or

PSA Changes	Minimum No. of determinations	Interval	Percentage increase over range of values
Androgen independent	3	\geq 1Week	25%
	2	\geq 2Week	

- Patients with histologically confirmed prostate cancer at MSKCC
- STEAP1 antigen positive tissue known from prior IHC testing or if STEAP1 status is not known archival sample will be sent to Genentech for IHC. Samples need to be positive, when feasible metastatic lesions will be tested preferentially rather than the primary.
- Performance status of 60 or higher (Karnofsky scale) (Appendix A)
- Ability to understand and willingness to sign a written informed consent document
- PSA levels to be taken within 2 weeks of antibody administration.

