Active lesions will be identified (Nuclear Medicine investigator and MM) based on conventional images and those thought to represent active disease based on review of the patients conventional images and treatment history (ie external radiation) will be considered as lesions for determination of antibody localization. A lesion will be considered present if there is greater localization than that expected based on blood pool distribution of the tracer. Given that at present we do not know the heterogeneity of the antigen between lesions or between primary and metastatic disease a patient will be considered positive if any of the active lesions are identified with the ^{89}Zr -DFO-MSTP2109A. We will, nonetheless tabulate the number of lesions and their status based on ^{89}Zr -DFO-MSTP2109A. When pathologic material that has been evaluated for the presence of STEAP1 is available for any specific lesion, we will correlate the presence of STEAP1 with imaging results.

Patients in Cohort 1A (and if performed Cohort 1B) will also have imaging at 4 time points post-injection to allow for selection of optimal imaging time and dosimetry determination. For these patients, top of skull to mid thigh scans will be acquired:

- Within one to four hours following injection of tracer on Day 1
- \sim 24 \pm 8 hours post-injection (Day 2)
- \sim 48–96 hours post-injection (once during Days 3–5)
- \sim 120–168 hours post injection (once during Days 6–8)

MEMORIAL SLOAN-KETTERING CANCER CENTER IRB PROTOCOL

IRB#:12-178 A(3)

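### A patient's imaging result rests on two different positivity rules and three descriptions of which lesions count, so the same scan can be read as positive or negative

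*Combined protocol and SAP*

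**What the plan says.** Three sections of the combined protocol and SAP describe how a patient's scan becomes a positive or negative result.

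- **Section 9.3 (Imaging).** Lesions found on conventional imaging are filtered before antibody localization is judged: "those thought to represent active disease based on review of the patients conventional images and treatment history (ie external radiation) will be considered as lesions". The patient-level rule has no percentage: "a patient will be considered positive if any of the active lesions are identified with the" tracer.
- **Section 12.0 (Outcome Assessment).** Lesions are scored from 1 to 5, and a consensus list keeps those scored 4 or 5 on imaging as sites of disease. No treatment-history filter is stated. One or two non-blinded readers, who can see clinical and laboratory data, identify the positive lesions.
- **Section 14.2 (Primary Objective).** A patient is "antibody-imaging-positive if 20% or more of the active lesions are detectable". The denominator is defined as follows: "Active lesion means any lesion that was identified by conventional imaging methods and clinical data at baseline". Among its reasons for a low threshold, the section says "we will consider positive any lesion based on conventional clinical imaging criteria, in which case some lesions considered positive may be false positive".

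Section 14.2 builds its decisions on this result. Four or more positive patients of 6 in Cohort 1A means the agent is feasible; otherwise Cohort 1B opens. Three negatives in Cohort 1B stop accrual. Feasibility is set at 75% of patients positive, and the Cohort 2 detection rate is the proportion positive among up to 15 patients.

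**The concern.** Two things are unsettled: which lesions form the denominator, and how many of them must be seen.

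The denominator matters in this disease for reasons that the protocol gives itself. Section 3.1 says of bone metastases: "Even if all tumor cells are destroyed, there may be no visible changes on standard scans". Section 17.4 expects many patients to have had radiation to the prostate or to bone. Eligibility (section 6.2) asks for "Visible lesions by either CT, bone scan or MRI consistent with metastatic disease", and visible is not the same as active. A treated lesion without viable tumor would not be expected to take up the antibody. Keeping it in the denominator lowers the detected fraction; the review in 9.3 could remove it.

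The threshold matters because one detected lesion is always enough under 9.3, but under 14.2 it is enough only if the patient has five lesions or fewer.

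With 6 patients per decision, one reclassified patient can turn 4 of 6 (feasible) into 3 of 6 (open Cohort 1B). Two analysts who each follow a section of the protocol could reach opposite cohort decisions from the same scans. Section 12.0 describes the consensus list as made after scoring and does not say that it is closed before the antibody results are known, so the choice could be made with the results in view.

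**Working it through.** **1. The plan's own figures (section 14.2).** With X positive patients of 6, Cohort 1B opens if X ≤ 3.
- True rate 40%: P(X ≤ 3) = 0.8208. The plan says more than 82%.
- True rate 75%: P(X ≤ 3) = 0.1694. The plan says less than 17%.
- Cohort 2 half-width: 1.96 × √(0.75 × 0.25 / 15) = 0.219. The plan says 22%.

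All three reproduce. They presuppose a single definition of a positive patient.

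**2. Any lesion versus 20%, same lesion set.** With d lesions detected of a active, 9.3 needs d ≥ 1 and 14.2 needs d ≥ a/5. The rules agree when a ≤ 5 and can differ when a ≥ 6. Example: d = 1, a = 10 gives 10%, positive under 9.3 and negative under 14.2.

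**3. Effect of the lesion set under the 20% rule.** Add k visible, inactive, undetected lesions to a patient who meets d/a ≥ 0.20. The result turns negative when d/(a + k) < 0.20, that is a + k > 5d, so k ≥ 5d − a + 1.

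| Detected / active | Added lesions needed | Result after adding |
|---|---|---|
| 1/5 = 20.0% | 1 | 1/6 = 16.7% |
| 2/10 = 20.0% | 1 | 2/11 = 18.2% |
| 2/8 = 25.0% | 3 | 2/11 = 18.2% |
| 1/3 = 33.3% | 3 | 1/6 = 16.7% |
| 5/10 = 50.0% | 16 | 5/26 = 19.2% |

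Under the any-lesion rule of 9.3, adding undetected lesions changes nothing. The dilution arises only where a percentage is applied.

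**4. What this could do to the Cohort 1A gate.** The documents give neither lesion counts nor the share that is inactive. The figures below are assumptions that show a range: lesions detected independently with probability q, all patients alike, and either no inactive lesion or one undetected inactive lesion per patient. Each cell gives P(patient positive), then P(Cohort 1B opens) = P(X ≤ 3 of 6).

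| Active lesions, q | Any lesion | 20%, active only | 20%, one inactive added |
|---|---|---|---|
| 5, 0.25 | 0.763; 0.15 | 0.763; 0.15 | 0.367; 0.86 |
| 5, 0.50 | 0.969; 0.001 | 0.969; 0.001 | 0.812; 0.084 |
| 10, 0.20 | 0.893; 0.02 | 0.624; 0.41 | 0.322; 0.91 |
| 10, 0.50 | 0.999; below 0.001 | 0.989; below 0.001 | 0.945; 0.003 |

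For example, with 5 active lesions and q = 0.25, at least one is detected with probability 1 − 0.75^5 = 0.763. With one inactive lesion added, two of six are needed, and the probability is 0.763 − 5 × 0.25 × 0.75^4 = 0.367.

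The definitions matter a great deal when per-lesion detection is near 20 to 25%, and little when it is 50%.

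**The case against.** The best defence is that the sections can be read together. Section 14.2 refers to clinical data as well as imaging, and treatment history is clinical data; the non-blinded readers in 12.0 also have clinical information. On that reading 14.2 is shorthand for the review in 9.3. This stands in part. A reader might infer that 14.2 counts every conventionally visible lesion and so flatly contradicts 9.3, but its wording does not go that far. It does not settle the matter either: 14.2 does not say what the clinical data are or whether treated lesions are removed, and its remark about false positives points towards an unfiltered list.

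Second, the threshold was set low partly because some conventional lesions may be false positives, so some dilution was foreseen. That is fair, and a reader should not infer a demonstrated bias towards negative results. But one fixed threshold cannot offset dilution that differs between patients.

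Third, the size is unknown. That stands: prior radiation is mentioned without frequencies, and radiation to the prostate says nothing about bone lesions.

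Fourth, a reader might infer that men with no active lesion will be enrolled, making the 20% rule 0/0, and that eligibility must change. Such a patient would need every visible lesion to be judged inactive. Section 9.3 does not exclude irradiated lesions automatically, and one entry route is protocol 11-016, whose criteria are not in the documents. A classification rule is enough.

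None of this answers the conflict between any lesion and 20%.

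**Conclusion.** The concern holds in two parts of different strength. The patient-level rule is in direct conflict: any active lesion in 9.3, at least 20% in 14.2. The lesion set is an unresolved ambiguity among 9.3, 12.0 and 14.2. Either can change a patient's status, and through it the Cohort 1A and 1B decisions, the 75% criterion and the Cohort 2 estimate.

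The arithmetic of reversal is exact: 5d − a + 1 added undetected lesions are needed, which is one at exactly 20% and 16 for a patient with 5 of 10 detected. The effect on the trial cannot be computed from the documents. The probabilities above rest on assumed lesion counts, independence between lesions and identical patients. The plan's stated operating characteristics are correct as arithmetic. The passages should be reconciled before the first cohort decision.

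**What to change.** 1. **One lesion set for the primary endpoint** in 9.3, 12.0 and 14.2: lesions scored 4 or 5 on conventional imaging and judged active by the non-blinded readers after the treatment-history review that 9.3 already describes.
2. **One patient-level rule:** the 20% rule, on which the decision rules in 14.2 are built, with 9.3 aligned to it.
3. **Timing:** close and date each patient's active-lesion list before the antibody scan results are known.
4. **Empty denominator:** state how a patient with no active lesion is classified and whether he counts among the 6.
5. **Sensitivity analyses:** report the 20% result based on all conventionally identified lesions, and the any-lesion proportion.

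No added criterion that a treated lesion must have grown since treatment is advised. Section 9.3 contains none, and it would sit badly with the protocol's own account of sclerotic lesions (sections 1.0 and 3.1) and of bone-scan flare (section 3.1.1).

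The cost is wording in three sections and a dated lesion list, with no extra patients or scans. There is a small downside: the denominator holds fewer lesions. Because 20% was chosen partly to allow for false-positive lesions, applying it to a filtered set makes the criterion somewhat easier to meet, and 14.2 should say so.
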